Study of the **OPT**imum Duration of **A**coustic Pulse Thrombo**LYS**is Proc**E**dure in the Treatment
of Acute Submassive **P**ulmonary **E**mbolism

OPTALYSE PE – UK Extension – Revision UK Version 7

Statistical Analysis Plan

Primary and Long Term Follow Up

Protocol Number: EKOS – 12

Clinicaltrials.gov: NCT02396758

Version 1; 08 November 2019 – UK Extension

Sponsor:

EKOS Corporation, a BTG International Group Company
[name]
[name]

A. PROTOCOL SYNOPSIS

Title:	Study of the OPT imum Duration and Dose of r-tPA of Acoustic Pulse ThromboLYSis ProcEdure in the Treatment of Submassive Pulmonary Embolism OPTALYSE PE – UK Extension – Revision UK Version 7
Design:	A randomized, parallel, multi-arm, multi-center study
Brief Device Description:	The EkoSonic® Endovascular System (EKOS) employs high frequency (2-3MHz), low power ultrasound to facilitate the delivery of thrombolytic agents to the intravascular treatment site in the pulmonary arteries. The Acoustic Pulse Thrombolysis (APT) Procedure means the clinical use of EKOS in combination with r-tPA administration
Purpose:	The objective of this study is to determine the optimum dose of thrombolytic and duration of the ultrasound procedure (together are defined as the APT Procedure) as a treatment for acute submassive PE.
Primary Efficacy Endpoint:	Change in the ratio of the measurement of the Right Ventricular to Left Ventricular diameter ratio (RV/LV) as measured by CTA from baseline to 48 hours after the start of the APT Procedure.

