Enrollment:	
OPTALYSE PE 101 subjects were randomized and 100 treated in the OPTALYSE PE study and were followed for one year.
 
OPTALYSE PE – UK Extension (OPTALYSE UK) Up to 120 additional subjects were planned to be enrolled in the UK Extension study to obtain up to 75 efficacy evaluable subjects (25 efficacy evaluable subjects enrolled and randomized in each of 3 treatment arms.). Due to slow enrollment and the ability for sites to participate in the KNOCKOUT study, the OPTALYSE UK sites were instructed to stop enrollment on May 1, 2019. 29 subjects were enrolled in OPTALYSE UK and sites were instructed to continue following subjects for one 1 year per the protocol.
 
Evaluable subjects are those who have RV/LV assessments within specified windows and scores available at baseline and at 48 hours from the start of treatment.
																			

A. PROTOCOL SYNOPSIS

Clinical Sites:	
OPTALYSE PE 19 centers within the United States and the United Kingdom enrolled into OPTALYSE PE.
 
OPTALYSE PE – UK Extension (OPTALYSE UK) Up to 10 centers located in the United Kingdom were planned for OPTALYSE UK. At the time enrollment was stopped, 5 sites had enrolled subjects into OPTALYSE UK.

Time Course:	
OPTALYSE PE Enrollment into OPTALYSE PE took place from June 2015 through November 2016 with 1 year follow-up.
 
OPTALYSE PE – UK Extension (OPTALYSE UK) Enrollment into OPTALYSE UK took place from October 2017 through March 2019 with 1 year follow-up.

B. SCHEDULE OF ASSESSMENTS - OPTALYSE UK

	Screening/ Baseline ¹	Post APT Procedure				Follow-up - Clinic Visit			
	Day -2 within -48 Hrs. of APT start	Day 0 within 4 Hrs. of APT end	Day 1 24 Hrs. ±6 hrs of APT start	Day 2 48 Hrs. ±6 hrs of APT start	Day 3 72 Hrs. of APT start or D/C ¹⁰	Day 30 ± 5 D	Day 90 ± 10 D	Day 365 ± 14D	Early Term ¹¹
Informed Consent	X								
Demographics	X								
Medical History, Physical Exam, & Risk Factors	X								
Vital Signs ^{2,3}	X	X	X	X		X	X	X	X
Electrocardiogram	X								
CTA	X			X					
Hemodynamics/SvO ₂ ⁴	Optional								
PESI/sPESI	X	X	X	X					
Echocardiogram ^{5,6}	X	X	X	X		X	X	X	X
Laboratory Tests ⁷	X	X		X					
Biomarkers: Troponin, BNP/NT-proBNP, lactate/lactic acid, and D-dimer	X			X					
6 Minute Walk Test (6MW)						X	X	X	X
QOL Assessment: PEmb-QOL; EQ-5D- 5L						X	X	X	X
Adverse/VTE/Bleeding Events		X	X	X	X	X	X	X	X
Anticoagulant medications ⁸	X	X	X	X	X	X	X	X	X
Concomitant medications ⁹	X	X	X	X	X	X	X	X	X

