2.3 Efficacy Analyses

2.3.1 Primary Efficacy Analysis

The primary efficacy outcome is the change in the RV diameter-to-LV diameter ratio, from Screening/Baseline to 48 ± 6 hours after the start of the APT procedure, as determined by CTA. For each treatment arm, the mean RV/LV ratio change will be compared to the historical control value of a 0.20 reduction for the heparin arm¹. For this study, a 1-sided $p < 0.15$ by t test rejecting a ≤ 0.20 reduction will be regarded as a positive sign for further investigating a treatment regimen. As an example, should the standard deviation be 0.41 as observed in the SEATTLE II study, with 25 evaluable subjects the 1-sided p value would be <0.15 if the mean RV/LV ratio reduction is 0.29 or higher. To limit the 3-arm total false positive error rate to 0.15, the Hochberg procedure² will be used for statistical testing.

The main primary endpoint analyses will be performed for the ITT Subject Set and the Evaluable Subjects subset.

To explore a potential increasing trend in RV/LV ratio reduction for treatment Groups 1 through 3 as defined in Protocol Synopsis, i.e. Group 1 having the least reduction and Group 3 having the most reduction, an exploratory regression analysis will be performed on both absolute change and percent change data from all 3 groups. The independent variables will include baseline RV/LV ratio value, the unilateral vs. bilateral PE indicator, and treatment groups 1 through 3 coded ordinally as 1, 2, and 3. This exploratory analysis will only be performed on the ITT Subject Set.

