2.5 Sample Size And Power Estimation

The primary efficacy endpoint for the study is the 48-hour decrease in RV/LV ratio. The Fasullo¹ study's heparin arm indicated a mean RV/LV ratio decrease of 0.20. Based on these results, we propose a mean

48-hour RV/LV ratio (absolute) decrease ≤ 0.20 as the null hypothesis for this study. Rejecting the null hypothesis with a 1-sided $p<0.15$ by t test will be regarded as a positive sign for further investigating a treatment regimen. For submassive PE subjects in the SEATTLE II study, a mean RV/LV ratio reduction of 0.43 was observed with a standard deviation of 0.41. Should these results be true for a regimen in the current study, with 25 evaluable subjects, the power to detect a positive signal is approximately 0.96.

The simultaneous power for the three treatment groups at the planned sample size of with $n=25$ evaluable per arm is approximately 0.88 by the Hochberg procedure².

Appendix 1: List of Tables (All summaries and analyses will be by treatment arm for the UK Extension portion of the study unless otherwise specified. Except for RV/LV ratio analyses, all p values are 2-sided. Analyses that will be conducted for the combined portions of the study (OPTALYSE PE plus UK Extension) as well as for the UK Extension alone and are indicated by an asterisk.)

Subject Set = ITT for (1) – (20) Unless Otherwise Specified

- 1) Enrollment by Site
- 2) Demographics
 - a) Age
 - b) Weight
 - c) BMI
 - d) Gender
 - e) Ethnicity (Hispanic vs. not Hispanic)
 - f) Race
- 3) Clinical History and Risk Factors
 - (a) – (v) on *Clinical History and Risk Factors CRF*.
 - a) Hypercholesterolemia
 - b) Congestive Heart Failure
 - c) Hepatic Insufficiency
 - d) Renal Insufficiency
 - e) TIA or Stroke
 - f) Active Cancer
 - g) Diabetes
 - h) Hypertension
 - i) Tobacco use
 - j) $BMI \geq 30.0$
 - k) COPD
 - l) History of Cancer in Remission
 - m) Family History of VTE
 - n) Chronic Inflammatory Disorders
 - o) Acute Infectious Illness within 30 Days of signing ICF
 - p) Atherosclerotic Cardiovascular Disease
 - q) Currently taking a Hormonal Contraceptive or Replacement Therapy
 - r) Osteoarthritis of Either Hip or Knee

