11) Core Lab RV/LV ratio from CTA: Baseline, 48 hours Post APT Start, absolute difference (Post-Procedure - Baseline) and percent change*

Summarize as continuous data for all above, i.e. n, mean, SD, median, minimum, maximum; provide 95% CI's for mean absolute and percent changes; provide 1-sided and 2-sided p values testing reduction ≤ 0.20 by t test for mean absolute change from baseline; provide same p values testing reduction ≤ 0 by t test for mean percent change from baseline.

All analyses above for RV/LV ratio by CTA will be repeated for the efficacy evaluable patient subset for ITT patients.

Lastly, repeat the above analyses for ITT patients as 6 arms, i.e. unilateral vs. bilateral for each of the 3 randomization arms.

Using continuous data from all 3 arms, perform increasing benefit trend analysis as described in the last paragraph of Section 2.3.1 and provide the 2-sided p value. (ITT only)

12) Core lab echocardiogram: Baseline, within 4 hours of APT end, 24 and 48 hours post APT start, Day 30, Day 90, Day 365 (procedure start date = Day 0) and change from baseline at all post-baseline time points (for continuous endpoints a-c below, besides summarizing as n, mean, SD, median, minimum and maximum at each of the 7 time points, also provide box-wisker plots for all time points on the same graph)*

- RV/LV ratio (perform same analysis at all time points as for the primary endpoint of RV/LV ratio as described in (11) above with the exceptions that testing a mean reduction of 0.20 applies to the 48 hours time point only and binary endpoint applies to \leq baseline vs. $>$ baseline only) (ITT)
- TAPSE (perform same analysis at all time points as for the primary endpoint of RV/LV ratio as described in (11) above, except mean absolute changes from baseline are tested against 0 as opposed to 0.20 and all p values are 2-sided and binary endpoint applies to \leq baseline vs. $>$ baseline only) (ITT)
- Estimated RVSP (perform same analysis at all time points as for the primary endpoint of RV/LV ratio as described in (11) above, except mean absolute changes from baseline are tested against 0 as opposed to 0.20 and all p values are 2-sided and binary endpoint applies to \leq baseline vs. $>$ baseline only) (ITT)
- IVC collapse with respiration (summarize as frequency and proportion at each time point and 2 \times 2 tables for changes from baseline, provide p values by McNemar's test) (ITT)

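### The SAP's power (0.96 per arm, 0.88 for three arms) and its 0.29 example are for 25 per arm; the UK-only tests have 29 subjects in all

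*SAP*

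**What the plan says.** SAP section 2.5 takes a mean RV/LV reduction of 0.43 with SD 0.41, a null of 0.20 or less, and a one-sided t test at 0.15. From these it states that "with 25 evaluable subjects, the power to detect a positive signal is approximately 0.96". It adds that the simultaneous power at the planned number "evaluable per arm is approximately 0.88 by the Hochberg procedure". Section 2.3.1 gives an example, also at 25 evaluable subjects with SD 0.41: the one-sided p value falls below 0.15 "if the mean RV/LV ratio reduction is 0.29 or higher". The Hochberg procedure holds the three-arm error rate at 0.15.

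The SAP is headed "Version 1; 08 November 2019". Its synopsis (Enrollment) says that "the OPTALYSE UK sites were instructed to stop enrollment on May 1, 2019" and that "29 subjects were enrolled in OPTALYSE UK", where up to 75 evaluable had been planned.

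The UK-only tests remain. Appendix 1 opens with "All summaries and analyses will be by treatment arm for the UK Extension portion of the study unless otherwise specified", and item 11, the CTA RV/LV ratio, says to "provide 1-sided and 2-sided p values testing reduction ≤ 0.20 by t test for mean absolute change from baseline". Item 11 carries an asterisk, so it is also run on the two study portions combined. Section 2.1 rules out imputation of missing efficacy data.

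**The concern.** The synopsis was brought up to date with the achieved enrolment; sections 2.5 and 2.3.1 were not. The SAP therefore specifies a by-arm test on the UK data, and the only power and example threshold it offers belong to a sample about two and a half times as large (75 against 29). It gives no UK split, no power or threshold at the achieved size, and no number per arm or power for the pooled test.

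A one-sided p below 0.15 is the stated signal for taking a regimen further. Someone who reads a UK arm that misses it against a power of 0.96 would take the miss as strong evidence against the regimen. At the achieved size it is weak evidence.

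**Working it through.** **Inputs** (SAP 2.5 and 2.3.1): null reduction 0.20, assumed reduction 0.43 (difference 0.23), SD 0.41, one-sided alpha 0.15, one-sample t test, three arms, Hochberg. Achieved UK total: 29 (SAP synopsis).

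**Formulas**
- Power = P(T > t(0.85, n−1)), where T is noncentral t with n−1 degrees of freedom and noncentrality (0.23/0.41)·√n.
- Threshold = 0.20 + t(0.85, n−1)·0.41/√n.
- Hochberg rejects all three nulls exactly when the largest p is below 0.15, so all-three power is the product of the three per-arm powers (independent arms).

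**Reproducing the SAP at n=25.** Noncentrality is 0.561 × 5 = 2.805 and power is 0.959. Cubed, this is 0.881. The threshold is 0.20 + 1.059 × 0.082 = 0.287. All three stated figures are confirmed.

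**Bounds that need no assumed split.** Three arms of 10 would need 30 subjects, so with 29 at least one arm has 9 or fewer. Without imputation the number analysed can only fall. At n=9 the noncentrality is 1.683, power is 0.722, and the threshold is 0.20 + 1.108 × 0.41/3 = 0.351. Over every split of 29, all-three power peaks at 10/10/9: 0.7526 × 0.7526 × 0.7217 = 0.409.

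**By arm size**

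| n in arm | Unadjusted power | Threshold | One-sided p if the observed reduction is 0.29 | 95% CI half-width |
|---|---|---|---|---|
| 25 | 0.96 | 0.287 | 0.14 | 0.17 |
| 12 | 0.80 | 0.329 | 0.23 | 0.26 |
| 10 | 0.75 | 0.343 | 0.25 | 0.29 |
| 9 | 0.72 | 0.351 | 0.26 | 0.32 |
| 8 | 0.69 | 0.362 | 0.28 | 0.34 |

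The threshold, p and half-width columns take the observed SD to be 0.41, as the SAP's example does. A larger arm gains only at the expense of another: all-three power is 0.40 at 12/9/8 and 0.39 at 13/8/8.

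**After Hochberg** (simulation; 10/10/9 assumed, every CTA pair usable)

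| Quantity | 10/10/9 | 25/25/25 |
|---|---|---|
| Per-arm power, all three regimens effective | 0.66 / 0.66 / 0.64 | 0.95 |
| All three arms positive | 0.41 | 0.88 |
| At least one arm positive, all effective | 0.89 | above 0.99 |
| Power of a lone effective arm | 0.52 (n=10), 0.48 (n=9) | 0.87 |

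**Losses to evaluability.** Protocol section 4 expected 30 enrolled per group to give 25 bilaterally treated evaluable subjects. Applying that ratio to the UK total as an assumption, 29 × 25/30 is about 24, or 8 per arm. Power is then 0.69 per arm and 0.687³ = 0.32 for all three, with a threshold of 0.36.

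**Pooled analysis.** Its arm sizes are not given. If the 100 earlier treated subjects fell in three equal arms, each pooled arm has about 33 + 10 = 43 and power above 0.99. If only a quarter of them fell in each arm, it has about 34 and power about 0.99. The threshold is about 0.27 in both cases.

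**The case against.** Nothing in the SAP is false. Each figure is tied to 25 evaluable subjects, 0.88 is expressly for the planned size, and 0.29 is offered as an example, not as a decision rule. The synopsis discloses the shortfall. The p values will come from the actual n and SD, item 11 already requires n, SD, a 95% CI and a pooled result, and enrolment is closed, so a new power figure cannot change the sample. The documents attach meaning only to a positive result; no passage drops a regimen for missing p<0.15. And the chance of at least one positive arm is still 0.89 at 10/10/9 if all three regimens work.

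All of these statements are correct, and they limit the point. No analysis is invalid, and imprecision will show in the tables. They do not remove it. The SAP was written when the planned size was known not to have been reached, and it still prescribes the UK-only tests with no other statement of what they can detect. The 0.89 concerns finding any signal, whereas the rule is applied to each regimen. The pooled analysis is additional and has no stated size or power.

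**Conclusion.** The concern holds and should be fixed. On the SAP's planning inputs, the UK-only tests have at least one arm with unadjusted power of 0.72 or less, against the stated 0.96, and all-three power of at most 0.41, against 0.88. In that arm the observed reduction must reach about 0.35 or more for p<0.15, against 0.29. These are best-case bounds: they depend on the assumed effect of 0.43 and SD of 0.41 but on no particular split, and unilateral treatment or missing or out-of-window CTAs can only lower the power.

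At 10/10/9 with all data usable, an arm with the assumed benefit misses the unadjusted signal 25–28% of the time, against 4% at n=25. Under Hochberg it misses 34–36% of the time if all regimens work (5% at n=25), and about 48–52% if it is the only one that works (13% at n=25). The split is an assumption, since the SAP does not give it.

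**What to change.** In SAP section 2.5, keep 0.96 and 0.88, labelled as original-plan values, and add:

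1. The UK number per arm, randomised and evaluable.
2. UK-only per-arm and all-three power at those numbers, from the same planning inputs and not from the observed effect. At 10/10/9 these would be 0.75/0.75/0.72 and 0.41; at 8 per arm, 0.69 and 0.32.
3. The number per arm and the power of the pooled analysis.

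In section 2.3.1, keep the 0.29 example at n=25 and add the threshold at the achieved n (0.34 at n=10, 0.35 at n=9, 0.36 at n=8).

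Optionally, add one sentence saying that a non-significant UK-only arm is not evidence of no effect and is to be read with the 95% CI and the pooled result that item 11 already requires.

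The cost is SAP wording only. No test, alpha level, analysis set or patient is affected; the stated UK-only figures become less favourable.

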2.2 General Methodology

All analyses will be performed separately for each of the treatment arms. Continuous measures will be summarized as n, mean, standard deviation, median, minimum and maximum. Categorical data will be summarized as frequency and percentage for each data category.

Where possible and indicated in Appendix 1 List of Tables , a pooled analysis will be performed with the OPTALYSE PE and OPTALYSE UK extension data combined. In each case, the same Analysis Subject Set for each population will be used.

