At select participating sites: In addition to the vital signs specified in Section 7.4, bedside vital signs including, systolic/diastolic blood pressure, heart rate, respiratory rate, capillary refill time and SpO2 will be recorded at the start of the APT Procedure, and at each 30 minute interval until 4 hours post-completion of the APT Procedure. Along with the echocardiograms specified in Section 7.7, limited echocardiograms performed at the bedside for RV/LV ratio measurements will be obtained hourly after the start of the APT Procedure through 4 hours post procedure.

Scatterplots of RV/LV ratio (y-axis) vs vital sign measures (x-axis) and of change in RV/LV ratio vs changes in vital sign measures will be presented to assess the correlation of change in clinical parameters (vital signs) with change in markers of RV strain (RV/LV ratio), and associated Pearson or Spearman correlation coefficients, where applicable.

Subject Set = Safety Subject Set for (19 – 23)

- 21) Major Bleeding Events within 72 hours of initiation of APT*
- 22) Technical Procedural Complications (*captured on the EkoSonic Device CRF as “Was this device successfully placed and used for treatment?”; make this a by-patient listing*)
- 23) Symptomatic Recurrent PE and Symptomatic Recurrent PE up to Day 365 (Confirmed by imaging)
- 24) All cause mortality up to Day 30 and all cause mortality up to Day 365 (*note: per AE and study exit CRFs*)
- 25) Adverse Events (*Run tables for AEs up to Day 30: AE start date ≤ Date of 30 Day Follow Up Visit per Follow-Up CRF*)
 - a) All reported events
 - b) Related to interventional procedure (not EKOS system)
 - c) Related to EKOS system
 - d) Related to thrombolytic drug
 - e) Related to anticoagulant drug
 - f) Bleeding events (*all site reported bleeding events, make tables for:*
-All reported bleeding events
-Those within 72 hours of APT start
-Those related to:
-interventional procedure (not EKOS system)
-EKOS system
-thrombolytic drug
-anticoagulant drug
 - g) SAEs

Also run analyses for (g) through Day 365, including those through 30 days.

26) Freedom from major harm occurring between enrolment and 30 days and assessed by the Safety Monitor using the following criteria:

- a. Mortality – all cause and PE related
- b. CV collapse: Defined as one or more of the following:
 - i. >40mmHg drop in SBP (for >15 minutes from documented blood pressure as an in-patient) despite IV fluid challenge and absence of new atrial arrhythmia.

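### In the SAP's safety list only 72-hour major bleeding is pooled with OPTALYSE PE; recurrent PE, mortality, bleeding and SAE tables stay in UK arms of about 10

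*SAP*

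**What the plan says.** The Appendix 1 header sets the default: "All summaries and analyses will be by treatment arm for the UK Extension portion of the study unless otherwise specified". The exceptions are "Analyses that will be conducted for the combined portions of the study (OPTALYSE PE plus UK Extension", and these are run "as well as for the UK Extension alone and are indicated by an asterisk". SAP 2.2 says "a pooled analysis will be performed with the OPTALYSE PE and OPTALYSE UK extension data combined", but only where possible and where Appendix 1 indicates it. The asterisk therefore decides what is pooled.

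In the Safety Subject Set list, item 21, "Major Bleeding Events within 72 hours of initiation of APT", carries the asterisk. Item 23, "Symptomatic Recurrent PE and Symptomatic Recurrent PE up to Day 365 (Confirmed by imaging", and item 24, "All cause mortality up to Day 30 and all cause mortality up to Day 365", do not. Nor do item 22 (technical complications, a by-patient listing), item 25 (adverse events, with bleeding under f and SAEs under g) or item 26 (freedom from major harm). SAP 2.4 pools nothing further and gives no reason for the difference.

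Among the efficacy tables, CTA RV/LV (11), echocardiography (12), modified Miller score (15), both quality-of-life scales (16) and the walk test (17) are marked. Items 12, 16 and 17 run to Day 365.

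On the data available, the SAP synopsis states that "101 subjects were randomized and 100 treated in the OPTALYSE PE study and were followed for one year". It also states that UK enrolment stopped with 29 subjects.

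**The concern.** Recurrent PE and mortality to Day 365 are named secondary safety outcomes, for which SAP 2.4 promises 95% Wilson intervals. Protocol 1.2 gives information on recurrent venous thromboembolism as a purpose of the 12-month follow-up, and says the extension was meant to raise the number of patients treated under each regimen. Reporting these outcomes only for the UK arms leaves that gain unused. When the SAP was dated (November 2019) recruitment had already closed at 29, so the small arms were known.

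What is at stake is precision. By-arm estimates from about 10 subjects are compatible with a very wide range of rates, while one-year follow-up on a further 100 treated subjects exists within the same programme.

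**Working it through.** **No stated figure to reproduce.** The documents give no precision or power for any safety outcome. The power of 0.96 in SAP 2.5 concerns the primary efficacy test, and this point does not depend on it.

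**Step 1: count the marks.** The safety list has six numbered tables, items 21 to 26. One of the six, item 21, has an asterisk.

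**Step 2: UK arm size.** 29 enrolled / 3 arms = 9.7, so about 9 or 10. No allocation ratio is stated; near-equal allocation is inferred from the equal target of 25 evaluable subjects per arm.

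**Step 3: pooled arm size (assumption).** OPTALYSE PE treated 100 subjects, but its split by arm is not given. I take 25 to 33 per arm: 100/4 = 25, which leaves room for subjects outside the three regimens, and 100/3 = 33.3. Adding the UK arms gives 25 + 9 = 34 to 33 + 10 = 43.

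**Step 4: Wilson 95% upper limit.** With z = 1.96 and p = x/n,

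upper = [p + z²/(2n) + z·√(p(1−p)/n + z²/(4n²))] / (1 + z²/n).

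With x = 0 this reduces to z²/(n + z²), where z² = 3.84:

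- n = 10: 3.84/13.84 = 27.8%
- n = 34: 3.84/37.84 = 10.2%
- n = 43: 3.84/46.84 = 8.2%

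| Subjects in arm | Upper limit, 0 events | Upper limit, 1 event | Chance of at least one event if true rate is 2%, 1 − 0.98ⁿ |
|---|---|---|---|
| 9 (UK) | 29.9% | 43.5% | 17% |
| 10 (UK) | 27.8% | 40.4% | 18% |
| 34 (pooled, assumed) | 10.2% | 14.9% | 50% |
| 43 (pooled, assumed) | 8.2% | 12.1% | 58% |

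The 2% rate is illustrative. With no events, pooling shortens the interval by a factor of 27.8/10.2 = 2.7 to 27.8/8.2 = 3.4.

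**Step 5: sensitivity to the split.** If only 30 subjects could be pooled in an arm, the zero-event limit would be 3.84/33.84 = 11.4%, still well under half the UK-only figure.

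**Step 6: is pooling within reach?** Item 21 is already pooled on the Safety Subject Set, and SAP 2.2 requires the same subject set in each population, so a combined safety set has to be built anyway. The pooled EQ-5D-5L table also has a rule for patients who died, so applying it in both portions requires knowing the deaths in both.

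**The case against.** **Pooling major bleeding first is a sound choice.** It is the primary safety endpoint, and Protocol 8.8 describes r-tPA harms as mainly bleeding. A reader might infer that the plan pools where precision is least needed and withholds pooling from the rarest events. The documents support neither. They give no event rates for this programme, and an SAE includes any death as well as any hospitalisation or prolonged stay, so SAEs cannot be rarer than deaths.

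**Pooling does not make the by-arm rates informative about low risks.** Protocol 1.1 likens submassive PE mortality to the intracranial haemorrhage rate under systemic lysis, for which it cites 1.9% and up to 3%. A pooled arm with no deaths would still leave 8 to 10% open, and at a true 2% rate it would show no event 42 to 50% of the time. This stands, and it limits what the change can achieve.

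**Comparability is not shown.** The OPTALYSE PE protocol, case report forms, event windows and coding are not among the documents. One year of follow-up does not prove that recurrence, bleeding and SAEs were defined and collected identically, nor that all 100 subjects were on these three regimens. This also stands, so the request has to be conditional.

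**The omission may be clerical.** Appendix 1 uses numbers 21 and 22 twice and labels the safety tables 19 to 23 although they run to 26. A mark lost in the public copy cannot be fully excluded, although other asterisks survive. Either way the list needs correcting, and nothing suggests that results were held back on purpose.

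**Item 26 is a different case.** SAP 1.3 and 2.3.2 list freedom from major harm as a secondary efficacy endpoint assessed by the Safety Monitor. Scoring it in OPTALYSE PE could require new adjudication.

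**Conclusion.** The point holds as a cheap improvement in precision. It is not an error that invalidates or biases any planned result, and the UK-only tables remain correct as they stand. As written, recurrent PE, mortality, and the bleeding and SAE tables are confined to UK arms of about 10, while one-year efficacy and quality-of-life data from both portions are combined, and no reason is given.

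The conclusion rests on near-equal UK allocation, on 25 to 33 OPTALYSE PE subjects per comparable arm, and on comparable event capture. Only the first two affect the figures, and the direction survives a smaller pooled arm. The interval figures apply directly to items 23 and 24, for which SAP 2.4 plans Wilson intervals. For 25(f) and 25(g), where it plans only frequencies and proportions, they show the precision that those proportions would have.

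A reader might conclude that pooling would settle the safety of each regimen. It would not: it removes much of the avoidable imprecision and leaves the rest.

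**What to change.** Add the asterisk to items 23, 24, 25(f) and 25(g) of the safety list, or state in SAP 2.2 why they are not pooled. Restrict the pooled rows to subjects treated with the Arm 1 to 3 regimens and to events defined and collected the same way in both portions. For each arm show UK, OPTALYSE PE and pooled rows side by side, with Wilson intervals for the subject-level proportions. Pool item 26 only if OPTALYSE PE events can be scored by the same criteria without new adjudication. Correct the duplicated item numbers and the range in the safety heading at the same time.

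The cost is some programming and harmonisation of event coding between the two portions. The pooled rows would also mix two recruitment periods (June 2015 to November 2016, and October 2017 to March 2019), which is why the separate rows should stay.
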